6 STUDY PROCEDURES AND SCHEDULE

The study will last six weeks. After consent and enrollment, patients in both the control and treatment groups will undergo STSG as scheduled. Promogran will be available in the operating room and applied by the operating surgeon (study or non-study surgeon) directly to the donor site of patients randomized to the treatment group. Patients in the control group will receive SOC dressings per the attending surgeon's clinical judgment. SOC dressings include a primary non-adherent dressing, a secondary gauze and transparent film or tape. The only difference between the two groups is the addition of Prisma in direct contact with the STSG donor site under the primary dressing in the treatment group.

Pain will be patient-reported using the visual analogue/Wong-Baker pain rating scale (VAS), which is reported on a scale from 0-10. Pain will be measured once at each of the following 12 time points: preoperatively, post-operatively (POD 1), and each subsequent postoperative day for ten days. After day 10, pain will be recorded by the assessing clinic provider during the weekly visits, until week six.

Patients will be followed daily while inpatient and weekly while outpatient for six weeks. The number of study visits will be between 6-10. The study visits will be combined with SOC visits and there will

be no study related procedures other than assessing pain at the donor site. Dressings will be changed and wounds assessed according to the standard of care at NYU Winthrop Hospital.

Screening Phase - Week -1 (within 7 days prior to treatment visit)

- Evaluation of eligibility for study inclusion
- Obtain informed consent
- Screening of inclusion/exclusion criteria
- Assign a unique subject identification number (SID).
- Randomize to treatment or control arm
- Perform physical examination and review medical, surgical, and medication histories.
- Perform a urine pregnancy test for females of reproductive potential.
- Collect demographic data including: date of birth, gender, race, ethnicity and tobacco use.
- Give patient pain diary and payment of \$35 patient stipend.

Treatment Phase - Day 0

- Ensure subject remains eligible prior to study product application.
- Confirm negative urine pregnancy test for females of reproductive potential prior to initial product application.
- Application of Prisma to STSG donor site for patients in the treatment group □ Record STSG donor site length and width
- Records all pain medications used in postoperative recovery room on POD 0

Follow-Up – Day 1 to 10

- Daily record of pain level in pain journal with the initial record once during 8am to 12pm and prior to each pain medication use
- Record time of any pain medication use
- Record pain of both donor and recipient STSG site

Follow-Up - Weeks 1 to 6 (6 week duration with 1 visit per week)

- Evaluation and record of STSG donor site – photography, length, width
- Record pain level of donor site
- Record any adverse events
- Collection of pain diary and second payment of \$35 stipend.

7 ASSESSMENT OF SAFETY

7.1 Adverse Events

Adverse Events (AEs) will be captured from the time the subject is randomized into the study. An AE is defined as follows:

- Any adverse change in the subject's medical status when compared with the subject's baseline condition, whether or not the event is related to the device or a procedure; or
- An exacerbation (either in frequency or severity) in a subject's pre-existing condition.

7.2 Classification of an Adverse Event

Known sequelae, judged by the Investigator to be associated with target wound procedures (e.g., pain or bleeding associated with STSG harvest) and/or the course of normal wound healing (e.g., slough or mild exudate) should not be recorded as an AE unless: 1) an additional treatment/procedure is required (e.g., use of a concomitant medication); or 2) the frequency, severity and/or duration deviates from the expected course. These include but are not limited to:

- Infection/sepsis
- Worsening of wound bed/failure to heal
- Increased chronic inflammation
- Allergic reaction

- Unexplained fever or chills
- Death
- Neurologic symptoms such as light headedness, headache
- Gastrointestinal symptoms including nausea and vomiting

An AE or suspected adverse reaction is considered "serious" if, in the view of either the Investigator or Sponsor, it results in any of the following outcomes:

- Death
- A life-threatening adverse event
- Inpatient hospitalization or prolongation of existing hospitalization
- A persistent or significant incapacity or substantial disruption of the ability to conduct normal life functions
- A congenital anomaly/birth defect

Important medical events that may not result in death, be life-threatening, or require hospitalization may be considered serious when, based upon appropriate medical judgment, they may jeopardize the patient or subject and may require medical or surgical intervention to prevent one of the outcomes listed in this definition.

Unanticipated adverse device effect is any serious adverse effect on health or safety, any lifethreatening problem or death caused by, or associated with a device, if that effect, problem, or death was not previously identified in nature, severity, or degree of incidence in the application, or any other unanticipated serious problem associated with a device that relates to the rights, safety, or welfare of subjects.

The Investigator will be asked to assess the severity of the AE using the following categories:

- Mild: Events require minimal or no treatment and do not interfere with the participant's daily activities.
- Moderate: Events result in a low level of inconvenience or concern with the therapeutic measures. Moderate events may cause some interference with functioning.
- Severe: Events interrupt a participant's usual daily activity and may require systemic drug therapy or other treatment. Severe events are usually potentially life-threatening or incapacitating.

7.3 Relationship to Study Agent

For all collected AEs, the clinician who examines and evaluates the participant will determine the AE's causality based on temporal relationship and his/her clinical judgment. The degree of certainty about causality will be graded using the categories below.

- Definitely Related: The relationship of the AE and the study device or the study procedure can definitely be established.
- Probably Related: While a clear relationship to the study device or to the study procedure cannot be established, the AE is associated with an expected AE or there is no other medical condition or intervention, which could explain the occurrence of such an event.
- Possibly Related: There is no clear relationship between the AE and the study device or study procedure; however, one cannot definitely conclude that there is no relationship.
- Unrelated Related: There is no relationship between the AE and the study device or study procedure. This may include but is not limited to the incident being an expected outcome of a

previously existing or concurrent disease, concomitant medication or procedure the subject experienced.

7.4 Expectedness

The PI will be responsible for determining whether an AE is expected or unexpected. An AE will be considered unexpected if the nature, severity, or frequency of the event is not consistent with the risk information previously described for the study agent.

The occurrence of an AE or SAE may come to the attention of study personnel during study visits and interviews of a study participant presenting for medical care, or upon review by a study monitor. All AEs including local and systemic reactions not meeting the criteria for SAEs will be captured on the appropriate RF. Information to be collected includes event description, time of onset, clinician's assessment of severity, relationship to study product (assessed only by those with the training and authority to make a diagnosis), and time of resolution/stabilization of the event. All AEs occurring while on study must be documented appropriately regardless of relationship. All AEs will be followed to adequate resolution.

Any medical condition that is present at the time that the participant is screened will be considered as baseline and not reported as an AE. However, if the study participant's condition deteriorates at any time during the study, it will be recorded as an AE. UPs will be recorded in the data collection system throughout the study.

Changes in the severity of an AE will be documented to allow an assessment of the duration of the event at each level of severity to be performed. AEs characterized as intermittent require documentation of onset and duration of each episode.

The PI will record all reportable events with start dates occurring any time after informed consent is obtained until 7 (for non-serious AEs) or 30 days (for SAEs) after the last day of study participation. At each study visit, the investigator will inquire about the occurrence of AE/SAEs since the last visit. Events will be followed for outcome information until resolution or stabilization.

All unresolved adverse events should be followed by the investigator until the events are resolved, the subject is lost to follow-up, or the adverse event is otherwise explained. At the last scheduled visit, the investigator should instruct each subject to report any subsequent event(s) that the subject, or the subject's personal physician, believes might reasonably be related to participation in this study. The investigator should notify the study sponsor of any death or adverse event occurring at any time after a subject has discontinued or terminated study participation that may reasonably be related to this study. The sponsor should also be notified if the investigator should become aware of the development of cancer or of a congenital anomaly in a subsequently conceived offspring of a subject that has participated in this study.

7.5 Unanticipated Problem Reporting

Incidents or events that meet the OHRP criteria for UPs require the creation and completion of an UP report form. It is the site investigator's responsibility to report UPs to their IRB and to the DCC/study sponsor. The UP report will include the following information:

- Protocol identifying information: protocol title and number, PI's name, and the IRB project number;
- A detailed description of the event, incident, experience, or outcome;
- An explanation of the basis for determining that the event, incident, experience, or outcome represents an UP;
- A description of any changes to the protocol or other corrective actions that have been taken or are proposed in response to the UP.

To satisfy the requirement for prompt reporting, UPs will be reported using the following timeline:

- UPs that are SAEs will be reported to the IRB and to the DCC/study sponsor within 5 business days of the investigator becoming aware of the event.
- Any other UP will be reported to the IRB and to the DCC/study sponsor within 5 business days of the investigator becoming aware of the problem.
- All UPs should be reported to appropriate institutional officials (as required by an institution's written reporting procedures), the supporting agency head (or designee), and OHRP within<insert timeline in accordance with policy> of the IR's receipt of the report of the problem from the investigator.

7.6 Reporting Procedures – Notifying the Study Sponsor

The study clinician will complete a SAE Form within the following timelines:

- All deaths and immediately life-threatening events, whether related or unrelated, will be recorded on the SAE Form and submitted to the DCC/study sponsor within 24 hours of site awareness. See Section 1, Key Roles for contact information.
- Other SAEs regardless of relationship will be submitted to the DCC/study sponsor within 72 hours of site awareness.

All SAEs will be followed until satisfactory resolution or until the site investigator deems the event to be chronic or the adherence to be stable. Other supporting documentation of the event may be requested by the DCC/study sponsor and should be provided as soon as possible.

As a follow-up to the initial report, within the following 48 hours of awareness of the event, the investigator shall provide further information, as applicable, on the unanticipated event or the unanticipated problem in the form of a written narrative. This should include a copy of the completed Unanticipated Problem form, and any other diagnostic information that will assist the understanding of the event. Significant new information on ongoing unanticipated adverse effects shall be provided promptly to the study sponsor.

8 Clinical Monitoring

Clinical site monitoring will be conducted to ensure that the rights and well-being of human subjects are protected, that the reported trial data are accurate, complete, and verifiable, and that the conduct of the trial is in compliance with the currently approved protocol/amendment(s), with Good Clinical Practice (GCP), and with applicable regulatory requirement(s).

Data safety monitoring will be done by the Clinical Research Coordinator. Events that will be monitored are infection at donor site, increasing pain at donor site, and allergic reaction to dressing. Monitoring will occur on a weekly basis once patients are enrolled. There are no predefined stopping points and reviews will be disseminated at the weekly research meeting.

9 STATISTICAL CONSIDERATION

9.1 Sample Size

A pilot study is limited in terms of statistical power due to its small sample size. As a result, no formal power computation was carried out. Proposed sample size (10 patients in each arm, a total of N=20) is obtained from a recruitment and cost feasibility point of view. The main aim of the study is to determine feasibility of the intervention, recruitment, randomization, retention a priori to a large full scale randomized clinical trial. No inferential decision will be made based on p-values; however the direction and size of the effect of the intervention on the outcomes observed will be critical for designing future randomized controlled trial where efficacy of the intervention will be determined.

9.2 Statistical Analysis Plan

Data will be summarized using descriptive statistics such as mean (standard deviation), median (Interquartile Range) based on the distribution of the continuous variables. Categorical variables will be presented as count (percentage).

9.3 Primary endpoint

Reducing pain at POD 1 was thought to be clinically important. Hence, the pain score at POD 1 will be compared between treatment groups using Wilcoxon rank-sum (Mann-Whitney) test. For demographic and other clinical covariates, we will test whether baseline characteristics are well balanced between two groups. If a baseline variable is not balanced or correlated with outcome ($r>0.30$), we will develop an ANCOVA model for POD 1 pain score and include it as a covariate in addition to baseline pain score and treatment groups.

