10 SOURCE DOCUMENTS AND ACCESS TO SOURCE DATA/DOCUMENTS		
.....	11	11 ETHICS/PROTECTIONI OF HUMAN
SUBJECTS.....	12	
11.1 Consent Procedures and Documentation	12	
11.2 Participant and Data Confidentiality	13	
12 DATA HANDLING AND RECORD KEEPING	13	
12.1 Study Records		
Retention	14	
12.2 Protocol Deviations	15	
14 SCHEDULE OF EVENTS.....	16	

LIST OF ABBREVIATIONS

AE	Adverse Event/Adverse Experience
CFR	Code of Federal Regulations
CRF	Case Report Form
DCC	Data Coordinating Center
DHHS	Department of Health and Human Services
DSMB	Data and Safety Monitoring Board
GCP	Good Clinical Practice
HIPAA	Health Insurance Portability and Accountability Act
ICF	Informed Consent Form
ICH	International Conference on Harmonisation

IRB	Institutional Review Board
MOP	Manual of Procedures
N	Number (typically refers to participants)
OHRP	Office for Human Research Protections
PI	Principal Investigator
POD	Postoperative day
SAE	Serious Adverse Event/Serious Adverse Experience
SOC	Standard of Care
STSG	Split Thickness Skin Graft
UP	Unanticipated Problem

Study number: s19-00437

Version: 3.2

PROTOCOL SUMMARY

Title	Impact of Promogran Prisma™ on pain of split-thickness skin graft donor sites compared to standard of care alone – a pilot study
Short Title	Impact of Prisma on donor site pain
Brief Summary	Twenty patients will be randomized into two groups: control and treatment. The control group will receive standard of care (SOC) dressings at the split thickness skin graft (STSG) donor site and the treatment group will receive Promogran in direct contact with the donor site in addition to SOC. SOC at NYU Winthrop Hospital includes, but is not limited to, xeroform or semi-occlusive adhesive dressings. The primary outcome is to assess the feasibility of evaluating Promogran in addition to SOC for the management of donor-site pain following STSG. The only difference between the two groups is the addition of Prisma in direct contact with the donor site under the SOC dressings in the treatment group.
Objectives	The primary objective of this study is to assess the feasibility of evaluating the use of a composite collagen, silver-oxidized regenerated cellulose matrix compared to the standard of care dressing on donor site pain for patients undergoing split-thickness skin grafting in preparation for a larger study.
Methodology	This is a prospective, randomized, open-label, single-center feasibility study.

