Endpoint	The primary endpoint of this feasibility study is to evaluate if using Promogran in addition to SOC is associated with a clinically meaningful difference in pain score (≥ 2 points on the visual analog pain scale) between the treatment and control arms on postoperative day (POD) 1.
Study Duration	Two years
Participant Duration	Six weeks
Duration of IP administration	One application
Population	Twenty patients; 10 in the intervention group and 10 in the control group. All genders, ≥ 18 years old, all demographics and geographic locations; scheduled to undergo STSG.
Study Sites	Single site: NYU Winthrop Hospital
Number of participants	20 participants
Study compensation	\$70. Two payments of \$35 will be given to participants – one at enrollment and one at collection of the 10-day pain diary.
Description of Study Agent/Procedure	Promogran Prisma™ is a composite collagen-silver-oxidized regenerated cellulose dressing that is a sheet applied topically to the STSG donor site.
Reference Therapy	The control group will receive a standard of care dressing on the STSG donor site (i.e., non-adherent dressing)
Key Procedures	Placement of either Prisma or standard of care dressing on the STSG donor site. Record daily pain score of the donor site for 10 days post-grafting. Return to clinic for weekly follow-up visits for 6 weeks.

Statistical Analysis	Proposed sample size (10 patients in each arm, a total of N=20) is obtained from a recruitment and cost feasibility point of view. For the primary endpoint, the pain score at POD 1 will be compared between treatment groups using Wilcoxon rank-sum (Mann-Whitney) test. The secondary endpoint, time from randomization to donor site healing, will be compared between treatment groups using time to event approach via Kaplan-Meier method.
----------------------	--

SCHEMATIC OF STUDY DESIGN

Total 20: Obtain informed consent. Screen potential subjects by inclusion and exclusion criteria. Perform physical examination and review medical, surgical, and medication histories. Perform a urine pregnancy test for females of reproductive potential. Collect (Day -7 - 0) demographic data including: date of birth, gender, race, ethnicity and tobacco use.

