5 STUDY ENROLLMENT AND WITHDRAWAL

Participants will be recruited from the NYU Winthrop Hospital Wound Care center, inpatient service, and other outpatient surgical services. Consent will be obtained by the principal and sub-investigators of the study.

5.1 Randomization:

Randomization will be performed 1:1 at enrollment. A computer generated randomized block assignment list will be given to the study coordinator. Each block of 2 or 4 subjects will contain an equal number of the two groups: 1) SOC, 2) Promogran+SOC. SAS PROC PLAN will be used to generate this list.

5.2 Inclusion Criteria:

1. Patient ≥ 18 years of age
2. Male or female
3. Patient scheduled to undergo STSG for any reason
4. Patient is able to provide informed consent and has read and signed the IRB-approved informed consent form.

5.3 Exclusion Criteria:

1. Active infection or history of radiation to the donor site
2. Patient has a known sensitivity to Promogran Prisma™ or silver
3. Elevated INR >3.0
4. Insensate at the donor site
5. Chronic narcotic use (>6 months of daily use)
6. Patient is currently pregnant and/or breastfeeding

The target number of enrolled patients will be 20, with 10 patients in the control and treatment groups, respectively. Patients will be allowed to withdraw consent at any time, with no adverse effect on the care received at NYU Winthrop Hospital.

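### Section 9.3 lets balance tests and an outcome correlation in the same 20 patients decide whether the POD 1 ANCOVA is run and what it adjusts for; fixing the model in advance is a minor, cheap improvement

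*Combined protocol and SAP*

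**What the plan says.** Section 9.3 and the Protocol Summary both name the Wilcoxon rank-sum test for POD 1 pain. In the Summary it is the only POD 1 comparison: "For the primary endpoint, the pain score at POD 1 will be compared between treatment groups using Wilcoxon rank-sum (Mann-Whitney) test".

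Section 9.3 then says of demographic and clinical variables that "we will test whether baseline characteristics are well balanced between two groups", and continues: "If a baseline variable is not balanced or correlated with outcome ($r>0.30$), we will develop an ANCOVA model for POD 1 pain score". The triggered variable is to "include it as a covariate in addition to baseline pain score and treatment groups".

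Section 9.2 promises descriptive summaries: "Data will be summarized using descriptive statistics such as mean (standard deviation), median (Interquartile Range)". Section 9.1 disclaims decisions based on p-values but adds that "the direction and size of the effect of the intervention on the outcomes observed will be critical for designing future randomized controlled trial".

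The following are not stated anywhere:
- a closed list of candidate covariates (sections 6 and 14 collect different demographics, and neither list is named as the candidate set);
- the balance test and its level;
- whether r means |r|, and whether it is taken over both arms or within arm;
- whether the ANCOVA supports the Wilcoxon test or replaces it;
- which score is the baseline pain score. Section 14 marks donor-site pain at screening and on Day 0; section 6 says only that it is measured before the operation.

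**The concern.** With 10 patients per arm, sample correlations and between-arm differences are noisy, so a rule that screens covariates on them often admits irrelevant ones. If r is computed over both arms together, it also contains the treatment effect. A covariate that by chance differs between arms in the same direction as pain is then more likely to pass, and adjusting for it removes part of a real effect.

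At stake is the effect estimate, which section 9.1 treats as an important product of the pilot. The ANCOVA is the only planned baseline-adjusted estimate. As written it may not be produced at all, and two analysts who follow section 9.3 could report different adjusted effects from the same data.

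**Working it through.** The plan has no figure of its own to reproduce: section 9.1 states that no power calculation was done, and the only number in the rule is 0.30.

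**Inputs from the documents:** 20 patients, 10 per arm (9.1); threshold 0.30 (9.3); 2-point difference of interest (4.2); seven demographics over sections 6 and 14 together (age or date of birth, gender, race, ethnicity, tobacco use, height, weight), of which three are numeric.

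**Assumptions:** k=3 or 7 candidates, independent normal noise; 5% balance test; SD 2.5, so that 2/2.5 = 0.8 SD; correlation of baseline with POD 1 pain 0 or 0.4. Figures are for signed r, with |r| in brackets.

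**1. One irrelevant covariate.** t = r√(n−2)/√(1−r²) = 0.30×√18/√0.91 = 1.334 on 18 df. The upper tail is 0.0994 and the two-sided probability 0.1988. Significance at two-sided 5% would need |r|>0.444, so the threshold is lenient.

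**2. At least one of k triggers.** 1 − [(1−p)×0.95]^k, treating the two triggers as independent:
- k=3: 1 − (0.9006×0.95)³ = 0.374 (0.559)
- k=7: 1 − (0.9006×0.95)⁷ = 0.664 (0.852)

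Simulation with a treatment effect present gives about 36-84% over the same range.

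**3. Effect on the estimate, r pooled over arms.** Simulation, 20,000 trials per case, true effect 0.80 SD. Range of means in triggered trials over baseline correlations 0 and 0.4:

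| k | signed r | \|r\| | shrinkage |
|---|---|---|---|
| 3 | 0.734-0.756 | 0.718-0.737 | 6-8% (8-10%) |
| 7 | 0.729-0.740 | 0.702-0.715 | 8-9% (11-12%) |

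For example, (0.80−0.734)/0.80 = 8%. An ANCOVA always run on treatment and baseline pain has mean 0.80 and SD 0.42-0.46.

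**4. Scale.** 6-12% of 2 points is 0.12-0.24 points. The standard error is 0.42-0.46 × 2.5 = 1.05-1.15 points. With a true effect of zero and k=7, the mean is 0.00 and the 5% rejection rate is 5.1-5.2% (5.2-5.5%).

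**5. What the unstated choices do.**
- r or |r|: the selected sets differ when some covariate has r below −0.30 and is not caught by the balance test. Per covariate this is 0.0994×0.95 = 0.0944, so 1−0.9056³ = 26% with k=3 and 1−0.9056⁷ = 50% with k=7. Simulation gives 25% and 49%, and the adjusted effects then differ by 0.34-0.37 points on average.
- Within-arm r, k=7: no shrinkage, but variance is 22-23% (28-30%) higher and CI coverage is 94% (93%).

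**6. Total error (MSE) of the rule relative to an ANCOVA always run on baseline pain alone.** Pooled r; where nothing triggers, the rule is given the baseline-pain ANCOVA, which section 9.3 does not in fact provide for.

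| Real predictors (r=0.4) among candidates | k=3 | k=7 |
|---|---|---|
| none | 1.06 | 1.14 (1.16) |
| one | 0.88-0.93 | 0.98-1.00 (1.00-1.02) |
| two | 0.73-0.79 | 0.82-0.85 (0.84-0.87) |

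The rule loses when all candidates are noise. It is level or better when a real predictor is among them and the fixed model leaves it out.

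**The case against.** This is a 20-patient feasibility study. Its p-values are nominal, no inferential decision rests on them, and the Wilcoxon comparison does not depend on the rule. A shift of 0.12-0.24 points against a standard error above 1 point cannot be seen in one trial. Where means are reported under section 9.2, their difference is already unbiased. The trigger rates assume that every candidate is noise and that baseline pain is not itself a trigger; counting it, at a correlation of 0.4, raises the rate to 79% (85%) with k=3 and 89% (95%) with k=7, so the ANCOVA would then usually be run. The number of candidates, the SD and the balance level are assumptions, and treating gender, race, ethnicity and tobacco use as independent continuous variables is a simplification.

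All of this stands, and it sets the size of the point. It does not remove it: which covariates enter still depends on the outcome data and on choices the plan leaves open.

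Three stronger readings are tempting and are not supported.
- *The rule undermines the primary comparison or inflates false positives.* The Wilcoxon test is unaffected, and rejection by the ANCOVA itself is near nominal.
- *The next trial will be sized on a biased estimate.* Section 9.1 does not say which estimate will be used.
- *A fixed model is more accurate.* Step 6 shows that this depends on whether strong predictors are named.

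**Conclusion.** The concern holds as a minor point. Section 9.3 makes the existence and content of the only planned adjusted estimate depend on balance tests and an outcome correlation in the same 20 patients. With 3 to 7 noise candidates and a 5% balance test the model is triggered in about 37-66% of trials (|r|: 56-85%). With pooled r and a true effect of 0.8 SD the adjusted effect in triggered trials shrinks by about 6-12%, well below its standard error. There is no shift if the true effect is zero or if r is taken within arm.

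The case for change is a fixed adjusted estimate that is always reported and free of selection bias, not assured greater accuracy. Calling the ANCOVA supportive is a proposal, since section 9.3 gives it no status.

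A reader might also infer that baseline pain is recorded after assignment, because randomization is placed at enrollment in section 5.1, in the screening phase in section 6 and, in the extracted table, on Day 0 in section 14. The documents do not establish this; they only leave the order open. That timing is a separate point to reconcile and adds nothing to the size of this one.

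**What to change.** In section 9.3:
- Delete the balance tests and the r>0.30 trigger, and present baseline characteristics descriptively.
- Keep the Wilcoxon test as the primary comparison.
- Always run one ANCOVA of POD 1 pain on treatment and baseline pain, and state that it is supportive. Add a further covariate only if it is named in 9.3 before any outcome data are seen.
- Report the adjusted and unadjusted mean differences with 95% CIs, whatever the result.
- Define baseline pain as one specified score recorded before randomization.

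The cost is a few sentences and no new measurements, since donor-site pain and demographics are already collected and baseline pain is already a term in the model.

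There are two downsides. If baseline pain is uninformative, which is possible because the donor site is intact before harvest, the variance of the estimate rises by about 6%. A strong predictor that nobody named stays unadjusted, and in that case the current rule can have lower total error.
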